Method	
After being reconstituted using the custom diluent provided with the investigational medicinal product (IMP), SGI-110 will be administered subcutaneously at a daily dose determined through calculation of each subject's body surface area (BSA) prior to administration of the IMP in each course, according to each cohort.
 
Each course will consist of 4 weeks (28 days). In Cohorts 1, 2, and 4, subjects will receive SGI-110 once daily for 5 consecutive days (Day 1 to Day 5), followed by a 23-day non-dosing period (Day 6 to Day 28). In Cohort 3, subjects will receive SGI-110 once daily for 10 days in total (SGI-110 will be administered for 5 consecutive days [Day 1 to Day 5], suspended for 2 days [Day 6 and Day 7], then administered for another 5 consecutive days [Day 8 to Day 12]), followed by a 16-day non-dosing period (Day 13 to Day 28).
 
The sponsor will confirm the incidence of dose-limiting toxicity (DLT) during the DLT evaluation period in each cohort and judge the transition to the next cohort based on the advice of the Independent Data Monitoring Committee. If the number of subjects exhibiting DLT within a cohort is <math>\geq 2/3</math> or <math>\geq 2/6</math>, then there will be no transition to the next cohort, and the maximum tolerated dose (MTD) will be determined as follows:
 
  
 <math>\geq 2/3</math> or <math>\geq 2/6</math> subjects with DLT	MTD	
   
 In Cohort 1	<math>< 36 \text{ mg/m}^2</math> in 5-day regimen	
 
 In Cohort 2	<math>36 \text{ mg/m}^2</math> in 5-day regimen	
 
 In Cohort 4	<math>60 \text{ mg/m}^2</math> in 5-day regimen	
  
 
If the incidence of DLT does not reach either <math>\geq 2/3</math> or <math>\geq 2/6</math> in any of the cohorts in the table above, the MTD will not be determined in this study. For Cohort 3, DLT will be evaluated but the MTD for 10-day regimen will not be determined from the incidence of DLT.
 
[Definition of dose-limiting toxicity] Dose-limiting toxicity shall be defined as any of the following AEs occurring during Course 1 for which there is a reasonable probability or possibility of a causal relationship with the IMP if it cannot be reasonably explained by underlying disease, intercurrent illness, or concomitant medications. The severity of AEs will be graded in accordance with Common Terminology Criteria for
	$\geq 2/3$ or $\geq 2/6$ subjects with DLT	MTD	In Cohort 1	$< 36 \text{ mg/m}^2$ in 5-day regimen	In Cohort 2	$36 \text{ mg/m}^2$ in 5-day regimen	In Cohort 4	$60 \text{ mg/m}^2$ in 5-day regimen

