### **3 Trial Plan**

#### **3.1 Trial Design**

This is a phase 1, multicenter, open-label study to evaluate the tolerability of SGI-110 in Japanese patients with relapsed or refractory AML after undergoing standard therapy or Japanese patients with AML aged 65 years or older who are not eligible for standard chemotherapy.

This trial consists of a screening period, DLT evaluation period, and withdrawal examination. Subjects who complete IMP administration and all observations during the DLT evaluation period, and who do not have any apparent progression of AML, will be permitted to continue treatment with IMP following the DLT evaluation period if they wish. The primary evaluation data for Cohorts 1, 2, and 4 will have a cutoff date of 31 May 2016 and the data for Cohort 3 will have a cutoff date of 30 Nov 2017. The period up until the data cutoff will be defined as the primary evaluation part. This will be followed by an extended treatment part to assess long-term safety, which will include those subjects on IMP treatment who have consented to participate in the extended treatment part. Transition from the primary evaluation part to the extended treatment part will take place at the start of the next course after the data cutoff.

Administration of the IMP will be started in Cohort 1 (36 mg/m^2 in 5-day regimen) and 3 subjects will receive the IMP in this cohort. If none of the 3 subjects has a DLT during the DLT evaluation period, the study will proceed to the next cohort. If one of the 3 subjects experiences a DLT, 3 additional subjects will be enrolled and DLTs will be evaluated in a total of 6 subjects. The study will proceed to the next cohort only if no more than one of the 6 subjects has a DLT. If the number of subjects exhibiting a DLT within a cohort is  $\geq 2/3$  or  $\geq 2/6$ , there will be no dose escalation.

In Cohort 2 (60 mg/m^2 in 5-day regimen) and Cohort 4 (90 mg/m^2 in 5-day regimen), DLTs will be assessed in the same manner. However, even if none of the first 3 subjects enrolled has a DLT, a total of 6 subjects will be enrolled in each of Cohorts 2 and 3 of which the dose has been determined as the recommended dose for a next phase study.

Based on the occurrence of DLTs, the tolerability at the recommended dose for a next phase study will be confirmed in Japanese subjects as well.

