### 3.4 Target Number of Patients

Maximum: 24 subjects

Cohort 1 (36 mg/m^2, 5 days): 3 to 6 subjects

Cohort 2 (60 mg/m^2, 5 days): 3 to 6 subjects

Cohort 3 (60 mg/m^2, 10 days [ie, 5-day administration twice, with a non-dosing period in-between]): 6 subjects

Cohort 4 (90 mg/m^2, 5 days): 3 to 6 subjects

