To perform pharmacodynamics (PD) evaluation of the extent of deoxyribonucleic acid (DNA) hypomethylation

3 Trial Design

This is a phase 1, multicenter, open-label study to evaluate the tolerability of SGI-110 in Japanese patients with relapsed or refractory AML after undergoing standard therapy or Japanese patients with AML aged 65 years or older who are not eligible for standard chemotherapy.

This trial consists of a screening period, dose limiting toxicity (DLT) evaluation period, and withdrawal examination. Subjects who complete investigational medicinal product (IMP) administration and all observations during the DLT evaluation period, and who do not have any apparent progression of AML, will be permitted to continue treatment with IMP following the DLT evaluation period if they wish. The primary evaluation data for Cohorts 1, 2, and 4 will have a cut-off date of 31 May 2016 and the primary evaluation data for Cohort 3 will have a cut-off date of 30 Nov 2017. The period up until the data cut-off will be defined as the primary evaluation part. This will be followed by an extended treatment part to assess long-term safety, which will include those subjects on IMP treatment who have consented to participate in the extended treatment part. Transition from the primary evaluation part to the extended treatment part will take place at the start of the next course after the data cut-off.

Administration of the IMP will be started in Cohort 1 (36 mg/m² in 5-day regimen) and 3 subjects will receive the IMP in this cohort. If none of the 3 subjects has a DLT during the DLT evaluation period, the study will proceed to the next cohort. If one of the 3 subjects experiences a DLT, 3 additional subjects will be enrolled and DLTs will be evaluated in a total of 6 subjects. The study will proceed to the next cohort only if no more than one of the 6 subjects has a DLT. If the number of subjects exhibiting a DLT within a cohort is $\geq 2/3$ or $\geq 2/6$, there will be no dose escalation.

In Cohort 2 (60 mg/m² in 5-day regimen) and Cohort 4 (90 mg/m² in 5-day regimen), DLTs will be assessed in the same manner. However, even if none of the first 3 subjects enrolled has a DLT, a total of 6 subjects will be enrolled in each of Cohorts 2 and 3 of which the dose has been determined as the recommended dose for a next phase study.

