6.5 Significance Level and Confidence Coefficient

No significance level or confidence coefficient will be set, since statistical tests and interval estimations will not be performed.

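### In Cohorts 1, 2 and 4 nothing closes enrolment when the second DLT falls on subject 4 or 5, so up to two more subjects are planned at a dose that has already failed the plan's own criterion

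*Protocol*

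**What the plan says.** The rule appears in the synopsis (Method), in Protocol 3.1 and again in SAP 3.

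- **Expansion.** After one DLT among the first 3 subjects, "3 additional subjects will be enrolled and DLTs will be evaluated in a total of 6 subjects". No condition is attached to what happens in subjects 4 and 5.
- **Escalation.** "The study will proceed to the next cohort only if no more than one of the 6 subjects has a DLT" (SAP 3; Protocol 3.1 has the same rule).
- **Consequence of two or more DLTs in 3 or in 6.** Protocol 3.1 says "there will be no dose escalation". The synopsis says "then there will be no transition to the next cohort, and the maximum tolerated dose (MTD) will be determined as follows", followed by one MTD row each for Cohorts 1, 2 and 4.
- **Filling the recommended-dose cohorts.** Even with no DLT in the first 3, "a total of 6 subjects will be enrolled in each of Cohorts 2 and 3" (Protocol 3.1). Cohort 3 has no MTD row and is outside this point.
- **Size.** Protocol 3.4 lists Cohorts 1, 2 and 4 each as "5 days): 3 to 6 subjects", with an overall "Maximum: 24 subjects".

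The neighbouring provisions are silent on entry within a cohort. Sponsor and monitoring-committee review in 3.1 concerns the move between cohorts. The only stagger, in 3.5, is between the first and second subject at each dose level. Section 8.2.2 has DLTs reported to the sponsor within 24 hours in principle, but attaches no enrolment action to the report.

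**The concern.** The plan accepts two DLTs in the first 3 subjects as enough to fail a cohort without filling it to 6. The same two DLTs among 4 or 5 subjects have no stated effect until the sixth subject has been evaluated. Any subject entered in between receives a dose that can no longer pass and contributes nothing to the transition or MTD decision. What is at stake is avoidable exposure of a small number of patients with limited treatment options, and a rule that two sites could apply differently. The integrity of the dose decision is not at stake.

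**Working it through.** **Inputs from the documents.** Expansion and escalation rules: Protocol 3.1 and SAP 3. Cohort sizes: Protocol 3.4. There is no error rate, power or interval to reproduce, since SAP 6.5 says "No significance level or confidence coefficient will be set, since statistical tests and interval estimations will not be performed". The one stated figure, the maximum of 24, is 4 cohorts × 6 subjects = 24 and reproduces.

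**Assumptions.** The documents give no true DLT probability p, so I take 0.10 to 0.50, with independent subjects. Subjects enter one at a time and each outcome is known before the next entry.

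**Step 1: is the decision fixed?** With 2 DLTs in 4 or 5 subjects, the final count in 6 is at least 2 whatever follows. The failing criterion is certain, the MTD row is determined, and the probability of escalating is the same whether or not the cohort is filled.

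**Step 2: how many planned subjects remain?** Second DLT in subject 4: 6 − 4 = 2. In subject 5: 6 − 5 = 1. In subject 6: none.

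**Step 3: Cohorts 1 and 4** (expansion only after 1 in 3).

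- P(1 in 3) = 3p(1−p)²
- P(second DLT at subject 4) = 3p(1−p)² × p
- P(second DLT at subject 5) = 3p(1−p)² × (1−p)p
- Expected remaining subjects = 2 × P(at 4) + 1 × P(at 5)

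At p = 0.30: P(1 in 3) = 3 × 0.30 × 0.49 = 0.441; at subject 4, 0.441 × 0.30 = 0.1323; at subject 5, 0.441 × 0.70 × 0.30 = 0.0926. The sum is 0.225 and the expected number is 2 × 0.1323 + 0.0926 = 0.357.

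**Step 4: Cohort 2** (filled to 6 after 0 or 1 in 3). The path from 0 in 3 adds (1−p)³ × p² at subject 5, with one subject remaining. At p = 0.30 this is 0.343 × 0.09 = 0.0309, giving 0.225 + 0.031 = 0.256 and an expected number of 0.357 + 0.031 = 0.388.

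| Assumed p | Cohorts 1, 4: probability | Cohorts 1, 4: expected subjects | Cohort 2: probability | Cohort 2: expected subjects |
|---|---|---|---|---|
| 0.10 | 4.6% | 0.07 | 5.3% | 0.08 |
| 0.20 | 13.8% | 0.22 | 15.9% | 0.24 |
| 0.30 | 22.5% | 0.36 | 25.6% | 0.39 |
| 0.40 | 27.6% | 0.45 | 31.1% | 0.48 |
| 0.50 | 28.1% | 0.47 | 31.3% | 0.50 |

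These are per cohort opened, before any of its outcomes is known. When the event occurs, about 1.5 to 1.7 planned subjects remain on average.

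**Not counted above.** If both of the first two subjects have a DLT, subject 3 is still planned. That has probability p², 1% to 25% over the same range.

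**The case against.** **No sentence tells anyone to continue after a second DLT.** This stands. The size range for these cohorts permits ending at 4 or 5, the criterion for 6 can be read as met once two of up to six have had a DLT, and the sponsor would normally hear of a DLT within a day. A sponsor might well stop. A reader might infer that the plan orders continued enrolment or contradicts itself. The documents do not go that far: they combine an unconditional expansion with the absence of a halt, which is a gap.

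**The avoidable number may be smaller.** This also stands. Subjects 4 to 6 may enter in parallel. The DLT window runs to the Day 29 examination and longer if Course 2 is postponed. A DLT defined by a delay of more than 4 weeks emerges only around Day 57 (29 + 28). Febrile neutropenia that resolves is classified after consulting the monitoring committee. The number avoidable in any one cohort is therefore 0 to 2.

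**Low DLT rates are plausible.** Protocol 1.2.2.1.1.1 and 6.1 report no DLT in overseas AML subjects on the 5-day regimen up to 125 mg/m², above the 90 mg/m² maximum here. That favours the lower rows of the table, without fixing the rate in Japanese patients.

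**The dates limit the benefit.** The primary evaluation part for these cohorts was scheduled to end on 31 May 2016, and the SAP is based on protocol version 8 of 13 Oct 2017. By the plan's own calendar, the change may now serve mainly to settle the rule and the DLT denominator.

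**More subjects give more safety data.** Protocol 11.5 gives that reason for a recommended-dose cohort. It does not give it for a cohort that has already failed.

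**Conclusion.** The point holds as a gap in the stopping rule with a modest effect. Under the sequential-entry assumption and assumed DLT rates of 10% to 50%, a second DLT falls on subject 4 or 5 in about 5% to 28% of cohorts (5% to 31% for Cohort 2), and about 0.07 to 0.5 subject per cohort could be spared on average. Parallel entry or late confirmation lowers this. Escalation and MTD are unaffected.

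Three stronger readings are tempting and are not supported:

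- **That the risk is 55% to 75%.** Starting from 1 in 3, p + (1−p)p does give 0.551 at p = 0.33 and 0.75 at p = 0.50. Those figures assume that the first DLT has already happened and use only high rates. Multiplying by P(1 in 3), 0.444 and 0.375, gives 24% and 28%.
- **That entry is slow enough for each outcome to be known before the next subject.** The 20 months from 01 Oct 2014 to 31 May 2016 are the whole primary evaluation part, including later courses, survival follow-up and waits between cohorts. They are not an accrual period.
- **That each extra subject delays the result by a 4-week DLT period.** Windows overlap under parallel entry, and the result is already determined.

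In Cohort 2 after 0 in 3, at most one further subject is affected, because the second DLT cannot come before subject 5.

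**What to change.** In the synopsis (Method), Protocol 3.1 and SAP 3, apply the existing threshold of 2 as soon as it is reached. Suggested wording: once a second subject in Cohort 1, 2 or 4 has a confirmed DLT, no further subject is entered in that cohort, and the existing no-transition rule and MTD table apply. In SAP 9.2, state that the denominator is the number of subjects evaluated for DLT in the cohort. The word confirmed is needed because some events become DLTs only after committee consultation. The rule concerns entry only and changes nothing for subjects already on treatment. It also closes the gap after two DLTs in the first two subjects.

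The cost is one sentence in each place. The threshold, the MTD table, the escalation probabilities and the maximum of 24 stay as they are. The downside is that a failed cohort may end with fewer than 6 evaluated subjects, and so with less safety and PK information at that dose. No planned test or interval is lost, since none is planned. If the sponsor wants those extra data from a failed cohort, the plan should say so and give the reason.

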## List of Abbreviations and Definition of Terms

### List of Abbreviations

Abbreviation	Expansion
ADL	Activities of daily living
AE	Adverse event
ALB	Albumin
ALP	Alkaline phosphatase
ALT	Alanine aminotransferase
AML	Acute myeloid leukemia
APL	Acute promyelocytic leukemia
AST	Aspartate aminotransferase
BED	Biologically effective dose
BSA	Body surface area
BUN	Blood urea nitrogen
BW	Body Weight
CMML	Chronic myelomonocytic leukemia
Cr	Creatinine
CR	Complete remission
CRF	Case report form
CRi	Complete remission with incomplete blood count recovery
CRp	Complete remission with incomplete platelet recovery
CSR	Clinical study report
CTCAE	Common Terminology Criteria for Adverse Events
CYP	Cytochrome P-450
DLCO	Diffusing capacity of the lung for carbon monoxide
DLT	Dose-limiting toxicity
DNMT	DNA methyltransferase
ECG	Electrocardiogram, electrocardiography
ECOG	Eastern Cooperative Oncology Group
EDC	Electronic data capture
EDTA	Ethylenediaminetetraacetic acid
FEV 1	Forced expiratory volume in the first second
GOT	Glutamate oxaloacetate transaminase
GPT	Glutamate pyruvate transaminase
GVHD	Graft-versus host disease
Hb	Hemoglobin
HBcAB	Hepatitis B core antibody
HBsAB	Hepatitis B surface antibody
HBV	Hepatitis B virus
HCG	Human chorionic gonadotropin
Hct	Hematocrit
HCV	Hepatitis C virus
hERG	Human ether-a-go-go related gene
HI-E	Hematological improvement of erythrocytes
HI-P	Hematological improvement of platelets
HIV	Human immunodeficiency virus
HNSTD	Highest non-severely toxic dose
ICF	Informed consent form
ICH	International Conference on Harmonisation of Technical Requirements for Registration of Pharmaceuticals for Human Use

Abbreviation	Expansion
IMP	Investigational medicinal product
IRB	Institutional Review Board
LDH	Lactate dehydrogenase
LINE-1	Long interspersed nucleotide element-1
LVEF	Left ventricular ejection fraction
M/E ratio	Myeloid/erythroid ratio
mCR	Marrow complete remission
MDS	Myelodysplastic syndrome
MTD	Maximum tolerated dose
MUGA	Multiple-gated acquisition
NE	Not evaluable
NOEL	No observed effect level
NYHA	New York Heart Association
PD	Pharmacodynamic(s)
PK	Pharmacokinetic(s)
PR	Partial response
PS	Performance status
PT	Preferred term
QTc interval	Corrected QT interval
QTcF interval	QT interval as corrected by Fridericia's formula
RBC	Red blood cell
SAE	Serious adverse event
SC	Subcutaneous(ly)
SOC	System organ class
T-Bil	Total bilirubin
TP	Total protein
UA	Uric acid
ULN	Upper limit of normal
US	United States
WBC	White blood cell
WHO	World Health Organization

**Definitions of Terms**

Term	Definition
Screen failure	A screen failure is a subject from whom written informed consent is obtained, but to whom the investigational medicinal product (IMP) is not administered.
Individual subject trial start date	The day of obtaining the subject's written informed consent.
Withdrawn subject	A subject who withdraws from the trial during Course 1 without completing dose-limiting toxicity (DLT) evaluation or who withdraws from the trial after completing DLT evaluation. (Subjects who withdraw during Course 1, which is the DLT evaluation period, and those who withdraw after the DLT evaluation will be distinguished.)
Individual subject trial discontinuation date	The day of the withdrawal examination to be performed within 5 days from the day when the investigator or subinvestigator determines that the subject is to be withdrawn from the trial.
Completer	A subject who receives the specified IMP during Course 1, completes examinations, and is evaluable for DLTs.
Individual subject trial completion date	The day when the examination scheduled for Day 29 of Course 1 is performed or the start day of Course 2, whichever is later.
Individual subject trial period	A period from the day of obtaining the subject's informed consent to the day of trial discontinuation. Does not include the follow-up or outcome investigation period.

**List of Pharmacokinetic Parameters**

Abbreviation and Term (Unit)		Expansion or Definition
$AUC_{\infty}$	ng·h/mL	Area under the plasma concentration-time curve from time zero to infinity
$AUC_{\infty}/D$	ng·h/mL/mg/m 	$AUC_{\infty}$ normalized by dose
$AUC_{24h}$	ng·h/mL	Area under the plasma concentration-time curve from time zero to 24 hours
$AUC_{24h}/D$	ng·h/mL/mg/m 	$AUC_{24h}$ normalized by dose
$AUC_t$	ng·h/mL	Area under the plasma concentration-time curve calculated to the last observable concentration at time t
$AUC_t/D$	ng·h/mL/mg/m 	$AUC_t$ normalized by dose
$AUC_{\%} \text{Extrap}$	%	Percentage of AUC due to extrapolation from $t_{last}$ to infinity ( $[AUC_{\infty} - AUC_t] / AUC_{\infty} \times 100$ )
$CL/F$	L/h, L/h/m 	Apparent clearance of drug from plasma after extravascular administration, L/h normalized by body surface area (BSA)
$CL/F/BW$	L/h/kg	$CL/F$ normalized in body weight
$C_{max}$	ng/mL	Maximum (peak) plasma concentration of the drug
$C_{max}/D$	ng/mL/mg/m 	$C_{max}$ normalized by dose
$\lambda_z$	h 	Apparent terminal-phase disposition rate constant (first-order)
$t_{1/2,z}$	h	Terminal-phase elimination half-life
$t_{last}$	h	Time of last measurable (positive) concentration
$t_{max}$	h	Time to maximum (peak) plasma concentration
$V_z/F$	L, L/m 	Apparent volume of distribution during the terminal ( $\lambda_z$ ) phase after extravascular administration, L normalized by BSA
$V_z/F/BW$	L/kg	$V_z/F$ normalized in body weight
$R_{n,ac} (AUC_{24h})$		Accumulation ratio of nth dose to first dose at regular administration for $AUC_{24h}$
$R_{n,ac} (C_{max})$		Accumulation ratio of nth dose to first dose at regular administration for $C_{max}$

## **1 Introduction**

### **1.1 Background of Trial Plan**

SGI-110 is a dinucleotide incorporating decitabine, an inhibitor of DNA methylation, with deoxyguanosine via a phosphodiester bond. Decitabine (Dacogen®) has been approved and marketed in the United States (US) for the treatment of myelodysplastic syndrome (MDS) and in the European Union for the treatment of acute myeloid leukemia (AML) in elderly patients.

DNA methylation is a conversion to 5-methylcytosine that occurs when cytosines in the CpG islands located in the gene promoter region are methylated, and this methylation regulates gene expression. It is believed that when DNA methylation occurs in the cancer suppressor gene promoter region, transcription of cancer suppressor genes is suppressed, which leads to cellular canceration. Since such DNA methylation is mediated by DNA methyltransferase (DNMT), a drug with DNMT inhibitory effect is expected to be effective against reduction in transcription activity of cancer suppressor genes and activation of cancer genes associated with DNA methylation by DNMT.

Decitabine is a typical drug with a DNMT inhibitory effect, and has been approved outside Japan as a treatment of AML and MDS owing to its DNA hypomethylation.

Decitabine is more quickly metabolized by cytidine deaminase. Since SGI-110 is a dinucleotide of decitabine and deoxyguanosine, it is cleaved into decitabine and deoxyguanosine. The cleaved decitabine is gradually released into plasma. Thus, plasma decitabine concentrations are maintained without acute elevation in plasma concentrations, resulting in prolonged exposure. Decitabine activity is S-phase dependent, and prolonged exposure is believed to result in increases in S-phase leukemia cells exposed to decitabine. Hence, SGI-110 is expected to be more effective than decitabine. Decitabine is assumed to form a covalent complex with DNMT, thereby directly inhibiting DNA synthesis. Nonclinical toxicity studies of decitabine have shown that increased exposure leads to cytotoxicity; therefore, the inhibition of DNA synthesis may be associated with an antitumor effect.

Acute myeloid leukemia is a highly diverse blood cancer characterized by clonal autonomous proliferation of immature bone marrow cells with impaired differentiation and/or maturation capacity. Abnormal proliferation of leukemia cells in the bone marrow results in marked inhibition of normal hematopoietic function, presenting various symptoms associated with decreased white blood cells (WBCs), anemia, and decreased platelets. Acute myeloid leukemia is a serious disease and would be fatal in a short

period of time because of infection or bleeding if not appropriately treated. Among adult leukemias, AML is most frequent; the prevalence rate of AML in Japan is estimated to be approximately 2 to 4 per 100,000 population, and patients with AML account for approximately 55% to 65% of all patients with leukemia. For the treatment of AML, an anthracycline (standard-dose idarubicin or high-dose daunorubicin) in combination with a standard dose of cytarabine is recommended as remission-induction therapy in patients with primary untreated AML. This treatment achieves complete remission in approximately 80% of patients, but approximately 70% of these patients experience relapse. Also approximately 15% of patients show resistance to the first remission-induction therapy (poor responders to first therapy). Many therapies have been attempted for these relapsed and treatment-resistant AMLs; however, no standard therapy has been established yet.

For elderly patients with AML, a standard intensive chemotherapy, if tolerated, is expected to achieve a better remission rate and survival. However, it is difficult to uniformly perform chemotherapy with intensity equivalent to that for treatment-naïve younger patients with AML because of patients' characteristics such as decreased organ function. Furthermore, the incidence of adverse drug reactions is generally high when chemotherapy is given to elderly patients with AML, and adverse drug reactions are likely to be severe. Thus, the indication for a standard intensive chemotherapy needs to be carefully determined. When standard therapy is deemed to be inappropriate based on the performance status (PS), complications, and/or karyotypic abnormalities before the start of therapy, patients are treated with low-dose cytarabine if they are treatable. Its therapeutic results are however hardly adequate, and new drugs are therefore awaited. Compared with intravenous decitabine, the pharmacokinetic (PK) profile of SGI-110 may be improved because of prolongation of exposure without acute elevation in plasma decitabine concentrations. Therefore, SGI-110 is assumed to more effectively treat elderly patients with AML.

As mentioned above, since SGI-110 has a better PK profile than that of intravenous decitabine, it may well be a novel drug for the treatment of elderly patients with AML and patients with relapsed or refractory AML for which no standard therapy has been established. Consequently, the sponsor has decided to develop SGI-110.

